#### 9.2 Secondary Safety Endpoint

The secondary safety endpoint of the study will be the subject self-reported values pertaining to pain/discomfort during treatment and comfort in wearing the aligners captured in the questionnaire. For this endpoint, a Visual Analogue Scale (VAS) with a Wong Baker face scale is used.

- 9.2.1 Subject comfort wearing aligners during treatment via visual analogue scales (VAS): This question is directed to the subject. "How comfortable were the aligners to wear during your treatment?" (VAS: 0 very comfortable 10 very uncomfortable).
- 9.2.2 Subject pain associated with new tooth movements during treatment via visual analogue scales (VAS): This question is directed to the subject.
  "Did you experience any pain associated with new tooth movement?" (VAS: 0 no pain 10 worst possible pain).

**CONFIDENTIAL:** The information in this study protocol is strictly confidential and is available for review to Investigators, study center personnel, the ethics committee, and the health authorities. It will not be disclosed to third parties without written authorization from the Sponsor, except to obtain informed consent from persons receiving the study treatment. Once the protocol is signed, its terms are binding for all parties.

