# 9.3 **Primary Efficacy Endpoint**

The primary effectiveness endpoint is the comparison between the treatment groups of the quantification of actual vs planned tooth movements using weighted Peer Assessment Rating (PAR) index.

• Planned percentage reduction in PAR Score (Planned Improvement of Malocclusion [PIM])

In addition comparison between treatment groups will also be performed for:

- Actual percentage reduction in PAR Score (Actual Improvement of Malocclusion [AIM])
- Percentage of Accuracy of Outcome

Quantification and comparison of expressed and programmed tooth movements will be conducted using to measure orthodontic treatment need and outcome, the built-in weighted PAR analysis tool of 3Shape Ortho System software (K152086).

- 9.3.1 The weighted PAR scores for each Digital Study Model (DSM) would be compared as follows:
  - Planned percentage reduction in PAR Score (Planned Improvement of Malocclusion [PIM]) = PAR Score TS- PAR Score TP / PAR Score TS \* 100
  - Actual percentage reduction in PAR Score (Actual Improvement of Malocclusion [AIM]) = PAR Score TS- PAR Score TF / PAR Score TS \* 100
  - Percentage of Accuracy of Outcome = 100% [(|PIM -AIM|/|AIM|) \*100%]

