# 9.4 Secondary Efficacy Endpoint

The secondary endpoint of this study will be to assess overall subject and dentist (Investigator) satisfaction with their treatment. This will be assessed through a questionnaire provided to both the dentist and the subject when treatment is completed. For this endpoint, a rating scale (1 very satisfied - 10 very unsatisfied) is used.

- 9.4.1 Doctor satisfaction with treatment results: "How satisfied are you with the results obtained?" (1 very satisfied 10 very unsatisfied).
- 9.4.2 Subject satisfaction with treatment results: This question is directed to the subject "How satisfied are you with the results obtained?" (1 very satisfied 10 very unsatisfied).

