#### 12.1 Statistical Sample Size and Power (provided as an example)

12.1.1 The current study is a controlled prospective study to determine the expressed movements demonstrated by investigational device, Nighttime Aligners for 10-12 continous hours per day/night compared to the control group, Daytime Aligners, which are worn for 20-22 hours per day.

**CONFIDENTIAL:** The information in this study protocol is strictly confidential and is available for review to Investigators, study center personnel, the ethics committee, and the health authorities. It will not be disclosed to third parties without written authorization from the Sponsor, except to obtain informed consent from persons receiving the study treatment. Once the protocol is signed, its terms are binding for all parties.

12.1.2 Sample size calculations for this study were determined using statistical software Minitab to ensure proper powering. The desired sample size per arm is 23 based on power calculations previously developed by Dentsply Sirona. The desired level of power is 90%. The desired confidence is 95% (p <0.05). Calculations are based on a standard deviation of 1, a power value of 0.9 and a detected difference of 1. The calculation also assumes a 2-sided, alpha = 0.05 level of significance.

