- Actual percentage reduction in PAR Score (Actual Improvement of Malocclusion [AIM]) = PAR Score TS- PAR Score TF / PAR Score TS \* 100
- Percentage of Accuracy of Outcome = 100% [(|PIM AIM|/|AIM|) \*100%]

Statistical analysis comparing the two treatment groups using the Wilcoxon rank sum test will pe performed. A two-sided p-value below

5% will be regarded as statistically significant. The null hypothesis of the study is that there is no difference between the two groups.

- 12.2.9 Additional comparisons between treatment groups may be performed and p-values presented using the Wilcoxon rank sum test. Wilcoxon signed rank test may be used for analysis within treatment groups over time.
- 12.2.10 Calculation of Spearman's rank correlation coefficients will be performed to elucidate the relationships between the accuracy of outcome with treatment duration, number of aligners, subject pain levels, and overall subject and doctor satisfaction for each group.
- 12.2.11 All methods used in this clinical study have been previously published and reviewed (Griffith 2021, Grünheid 2022). All data in this clinical study will be analyzed by an independent contractor to remove bias. Any adjustments or modifications to these methods will be duly documented and reported.

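### One 5% rule and one study null cover three PAR measures, with nothing to say which one decides or how split results are read

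*Combined protocol and SAP*

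**What the plan says.** **Synopsis, Effectiveness Assessments.** Efficacy of the Nighttime Aligners is to be shown by the absence of a statistically significant difference from the Daytime Aligners in expressed versus programmed movement. No margin is given.

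**Section 9.3.** The primary endpoint is the between-group comparison of actual with planned movement on the weighted PAR index. PIM is the one bullet directly beneath that sentence. AIM and Percentage of Accuracy follow under a separate line: "In addition comparison between treatment groups will also be performed for" these two.

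**Section 12.2.8.** All three measures are listed together. The groups are then compared by Wilcoxon rank sum test, with this cut-off for the two-sided p: "5% will be regarded as statistically significant. The null hypothesis of the study is that there is no difference between the two groups". The rule is not attached to any one of the three.

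**Section 12.2.9.** "Additional comparisons between treatment groups may be performed and p-values presented using the Wilcoxon rank sum test". The comparisons are not listed.

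**Secondary endpoints.** Section 9.2: "The secondary safety endpoint of the study will be the subject self-reported values pertaining to pain/discomfort during treatment and comfort in wearing the aligners". Section 9.4: "The secondary endpoint of this study will be to assess overall subject and dentist (Investigator) satisfaction with their treatment". That makes four ratings, and no test is assigned to any of them. Section 12.2.2 makes descriptive statistics the default where nothing else is stated.

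The plan does use primary and secondary labels. It gives no testing order, alpha allocation, exploratory label or rule for split PAR results.

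**The concern.** One null needs one deciding result, or a stated rule for combining several. Here there are three candidates and no rule, so the same data can support opposite conclusions.

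Because the success claim rests on non-significance, the two possible readings err in opposite directions:

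- **A non-significant measure may be cited.** A real shortfall with the test device then gets extra chances to be passed over. This is the direction that favours the success claim.
- **Any significant measure counts as a difference.** Equal devices are then called different more often than the stated 5%. This works against the success claim.

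Section 12.2.1 adds to the exposure. The sponsor and investigators are unblinded and may analyse data periodically, so all three results could be seen before one is put forward as the answer.

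**Working it through.** **1. The plan's own figure.** Section 12.1.2 gives the size: "The desired sample size per arm is 23 based on power calculations previously developed by Dentsply Sirona". Its inputs are stated as follows: "Calculations are based on a standard deviation of 1, a power value of 0.9 and a detected difference of 1". The error rate is set in a further sentence: "The calculation also assumes a 2-sided, alpha = 0.05 level of significance".

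- Normal approximation: n = 2 × (1.960 + 1.282)² × 1² / 1² = 21.0, rounded up to 22 per arm.
- Two-sample t-test: 22.02, rounded up to 23. Power at 23 per arm is 91.2%.

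The 23 is reproduced. It is the size for one comparison at 5%, on a scale the plan does not name, so it does not identify the deciding measure.

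**2. What each measure contains** (12.2.8, with the brackets and minus sign that the formulas imply).

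- PIM = (TS − TP)/TS × 100
- AIM = (TS − TF)/TS × 100
- Accuracy = 100 − |PIM − AIM|/|AIM| × 100

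PIM has no TF term. If the two arms are planned alike, its test is non-significant in about 1 − 0.05 = 95% of trials whatever the outcome.

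Write AIM = f × PIM, where f is the achieved fraction of the planned improvement. For f above 0, |PIM − AIM|/|AIM| = |1/f − 1|. Accuracy then depends on f alone, while AIM also carries the spread in PIM. With PIM = 80:

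- f = 0.80: AIM = 64, Accuracy = 100 − 16/64 × 100 = 75.0
- f = 0.70: AIM = 56, Accuracy = 100 − 24/56 × 100 = 57.1

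Both fall, but with different noise around them, so their p-values can land on opposite sides of 5%.

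**3. If a non-significant measure may be cited.** The simulations use the plan's formulas and the Wilcoxon test. The inputs are assumptions, not in the documents: baseline PAR about 16, planned reduction about 80%, achieved fraction 0.70 v 0.80, SD 0.2. The ranges reflect differing assumed distributions.

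| Result under the assumed shortfall | 23 per arm | 50 per arm |
|---|---|---|
| AIM and Accuracy give opposite verdicts | 14-17% | 17-20% |
| PIM non-significant | about 95% | about 95% |

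In one set at 50 per arm, AIM was non-significant in 44% of trials, Accuracy in 39%, and at least one of them in 50%. Both were therefore non-significant in 44 + 39 − 50 = 33%, and the two disagreed in 50 − 33 = 17%. Free choice between AIM and Accuracy raises the chance of passing over the shortfall from 39-44% to 50%. If PIM may be cited too, it is at least about 95%.

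**4. If any significant measure counts, equal arms.** For independent tests, 1 − 0.95³ = 0.143 and 1 − 0.95⁷ = 0.302. The documents give no correlation, so a range is shown:

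| Tests | Method | ρ = 0 | ρ = 0.5 | ρ = 0.9 |
|---|---|---|---|---|
| 3 | Normal statistics | 0.142 | 0.126 | 0.083 |
| 3 | Wilcoxon, 23 per arm | 0.143 | 0.126 | 0.087 |
| 7 | Normal statistics | 0.302 | 0.230 | 0.114 |
| 7 | Wilcoxon, 23 per arm | 0.304 | 0.234 | 0.122 |

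The Wilcoxon results at 50 per arm are nearly the same. Building the three measures from their formulas under assumed distributions gives about 10-13% for any of three. AIM and Accuracy alone give about 7.5% (0.076-0.077 in simulation).

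**5. If all three must be non-significant.** With independent tests, equal arms pass in 0.95³ = 0.857 of trials. Success becomes harder, and multiplicity does not inflate false success. The plan does not state this rule either.

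**The case against.** The strongest reply is that a false-positive PAR difference counts against the test device, so an inflated family-wise rate is not an error in the sponsor's favour. That stands. The error that matters for the success claim is the one in step 3, which a family-wise rate does not measure.

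It can also be said that the plan is not without structure. Sections 9.1 to 9.4 label endpoints primary and secondary, and 9.3 brings in AIM and Accuracy as additions. That stands as well: a reader might infer that there is no hierarchy at all, and the text does not support that. But the labels do not finish the job. The one measure placed under the primary sentence, PIM, cannot register outcome, and 12.2.8 then puts all three under the same rule.

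A third reply is that the secondary ratings are not planned tests. This is correct. Section 12.2.2 makes them descriptive by default, 12.2.9 is optional, and the 5% sentence closes 12.2.8 rather than 12.2.9. A reader might infer that seven tests at full alpha are planned, or that a superiority claim on comfort or satisfaction is intended. The documents support neither.

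Finally, 12.2.7 has an external evaluator score PAR, and 12.2.11 gives the analysis to an independent contractor. Both help against bias in measurement and execution. Neither says which of three correctly computed p-values answers the study null.

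**Conclusion.** The point holds in limited form. Section 12.2.8 does not tie its 5% rule or the study null to one PAR measure, and it gives no reading for discordant results. With non-significance as the success criterion, the conclusion can turn on which p-value is cited.

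Size: AIM and Accuracy disagree in about 14-20% of trials under the assumed 0.70 v 0.80 shortfall, and PIM is non-significant in about 95% if the arms are planned alike. On an any-significant reading, equal arms are called different in about 8-14% of trials for three tests (correlation 0.9 to 0), or about 7.5% for the two measures that use TF. Seven tests, at about 11-30%, is the most the plan permits for these three measures and four ratings.

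A reader might infer a single study-wide false-positive rate of about 12-23%. The documents do not support that figure: it is the correlation-0.5 case for three to seven tests and presumes a rule that any significant result counts. Nor does the split rate show that AIM and Accuracy generally disagree; it belongs to one assumed scenario.

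This point takes the synopsis success criterion as it stands. Whether non-significance without a margin can support equivalence is a separate question.

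**What to change.** In 12.2.8, tie the 5% rule and the study null to one named PAR contrast that uses TF. State that the other PAR measures are supportive and cannot override it, whichever way they fall. Align 9.3 and the synopsis so that the same contrast is named throughout.

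As a smaller addition, state in 12.2.9 that any further p-values are exploratory and are reported with effect estimates and unadjusted 95% confidence intervals. Leave pain and comfort unadjusted: they are safety data, and adjustment would make harm harder to see.

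The cost is two or three sentences in 12.2.8 and 12.2.9, plus the matching wording in 9.3 and the synopsis, with no new data, subjects or procedures. The downside is that the sponsor gives up statements of statistical significance outside the deciding contrast. The contrast should be fixed before any of the periodic looks at unblinded data that 12.2.1 allows.

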# 12.3 Safety Analysis

- 12.3.1 As this is a non-significant risk study, the Sponsor does not intend to use a Data Safety Monitoring Board for this clinical study.
- 12.3.2 Safety aspects of the investigational device will be evaluated in terms of related adverse events (AEs) and serious adverse events (SAEs) documented during the course of treatment beginning at the time of application of the device through the time of completion of the treatment period; i.e., the time of removal of the final treatment aligner.
- 12.3.3 Evaluation of adverse events will be based on the risk management file and known risks/harms documented by Sponsor for aligner systems (e.g. design / process FMEAs, harms libraries, historical complaint files and post-market surveillance data).

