# 1. STUDY OBJECTIVES

# 1.1 **Primary Objective:**

The primary efficacy objective of this study is the comparison between groups of the quantification of actual vs planned tooth movements. Changes in tooth position from pre-treatment baseline to end of treatment results will be measured for both Daytime Aligners (control) and Nighttime Aligners (test).

The safety objective of the study will be the incidence of (device or dental) related AEs associated with the planned investigational treatment, in comparison to the incidence of AEs associated with control treatment.

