#### 9. ENDPOINTS

# 9.1 **Primary Safety Endpoint**

The primary safety endpoint of the study will be the incidence of (device or dental) related AEs and SAEs associated with the planned investigational treatment, compared to the incidence from treatment with the control device.

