# 11. ADVERSE EVENTS AND SERIOUS ADVERSE EVENTS

#### 11.1 Adverse Event (AEs)

- 11.1.1 All adverse events must be reported to the divisional complaint officer and regulatory compliance.
- 11.1.2 All Adverse Events (AEs) will be documented and recorded by the Investigator in the eCRF throughout the study period.
  - AE is defined as: Any untoward medical occurrence, unintended disease, effect or injury, or untoward clinical sign in a subject, whether related to the investigational product or not.
  - For example, a rash, bleeding, or blistering appearing on the soft tissue in contact with the investigational device.
  - Another example is clinically significant root resorption.
- 11.1.3 All adverse events shall be reported for that particular study subject's

appointment.

- This documentation should list the event, the cause of the event if known, consequences and resulting actions by the Investigator, or designee, and any other medically pertinent information.
- Where possible, a diagnosis rather than a list of symptoms should be given.
- The intensity to be recorded is the worst intensity experienced during the course of the event. The Investigator should complete all related information, including date(s) of onset, severity, corrective therapies given, outcome, and professional opinion as to whether the AE had a relationship to the investigational device.
- 11.1.4 The Center of Clinical Research (CoCR) team must make the determination of relationship to the investigational device for each recorded AE in the corresponding **eCRF**. The CoCR should decide whether there is a reasonable possibility that the event may have been caused by the investigational device.
- 11.1.5 If there is any valid reason, even if undetermined or untested, for suspecting a possible cause-and-effect relationship between the investigational device and the occurrence of the AE, then the AE should be considered "possibly" or "probably related".
- 11.1.6 Otherwise, if no valid reason exists for suggesting a relationship, then the AE should be classified as "unrelated". The following guidance may also be helpful:
  - Unrelated: There is no medical evidence to suggest that the AE is related to the investigational device. The AE can be readily explained by the subject's underlying medical condition or concomitant therapy or lacks a plausible temporal relationship to investigational device.

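### The Safety Analysis (12.3) does not plan the comparison with control that defines the primary safety endpoint, and relatedness is graded only to the investigational device

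*Combined protocol and SAP*

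**What the plan says.** All references are to the combined protocol and SAP.

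- **Objective and endpoint.** Section 1.1 sets the safety objective as AE incidence under the investigational treatment "in comparison to the incidence of AEs associated with control treatment". Section 9.1 defines the primary safety endpoint as "incidence of (device or dental) related AEs and SAEs associated with the planned investigational treatment, compared to the incidence from treatment with the control device".
- **Analysis.** Section 12.3 has three items. 12.3.1 says there will be no safety monitoring board. 12.3.2 begins "Safety aspects of the investigational device will be evaluated in terms of related adverse events (AEs) and serious adverse events (SAEs" and gives the time window, from first application to removal of the last aligner. 12.3.3 states that "Evaluation of adverse events will be based on the risk management file and known risks/harms documented by Sponsor for aligner systems", with "design / process FMEAs, harms libraries, historical complaint files and post-market surveillance data" as examples.
- **Relatedness.** Section 11.1.4 gives the sponsor's clinical research team the "determination of relationship to the investigational device for each recorded AE". Sections 11.1.5 and 11.1.6 define four grades, from unrelated to related, all by reference to the investigational device.
- **General rules.** Section 12.2.2 provides frequencies and percentages for categorical variables by default, with p-values and confidence intervals where appropriate. Section 12.2.9 permits, but does not require, further between-group comparisons by the Wilcoxon rank sum test.

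**The concern.** A primary endpoint that is comparative by definition needs an analysis that makes the comparison. Section 12.3 names no control arm, analysis set, denominator, incidence measure, between-arm estimate or interval. It also omits the device-or-dental qualifier from 9.1.

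The comparison matters for this product. Section 7.1.1 says that treatment delay and discomfort become more probable with reduced wear, and 11.1.9 lists gum pain, inflammation, redness, allergic reaction and root resorption as known effects of orthodontic treatment. Most events are therefore likely to be of known types. The useful question is whether they occur more often with Nighttime than with Daytime aligners. Complaint and post-market files cannot answer it, because they are not collected in the way AEs are collected at scheduled visits in this trial.

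The sponsor and investigators are unblinded and may analyse data periodically (12.2.1). An analysis left open could thus be chosen after the data have been seen. The trial is meant to support substantial equivalence including safety (Synopsis, Objective), so the safety comparison is part of the claim.

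**Working it through.** **Step 1. Endpoint against analysis.**

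| Element | 1.1 and 9.1 | 12.3 |
|---|---|---|
| Arms | Test and control | Investigational device only |
| Events | Device- or dental-related AEs; SAEs (9.1) | Related AEs; SAEs |
| Measure | Incidence | Not stated |
| Reference | Control device | Sponsor risk file and known harms |
| Denominator | Not stated | Not stated |
| Estimate and interval | Not stated | Not stated |

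**Step 2. Can the 9.1 incidence be computed from the AE page?** Section 11.1.2 records every AE, related or not, so the events are in the database in both arms. The relatedness scale has no wording for the control device. The abbreviation list equates investigational product with investigational device and does not mention the control. Section 11.3.1, by contrast, expressly extends device deficiencies to the comparator. There is no dental-related category anywhere in 11.1. As written, the control-arm count of device-related AEs and the dental-related count in either arm are both undefined.

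**Step 3. Do the general rules supply the comparison?** 12.2.2 would yield frequencies by default, but it names neither AEs nor a subject-level incidence, and it cannot define the missing classification. 12.2.9 is optional and specifies no effect estimate.

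**Step 4. The plan's own sizing figure.** Section 12.1.2 gives 23 per arm from a difference of 1, SD 1, power 0.90 and two-sided alpha 0.05. The normal approximation gives 2 × (1.960 + 1.282)² × 1²/1² = 21.0, rounded up to 22. The two-sample t-test solution is 22.02, rounded up to 23, with power 91.2%. The figure reproduces, but it concerns a continuous outcome. Section 4.2 makes 23 the minimum number of evaluable, compliant completers, so it is not a safety denominator.

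**Step 5. Precision of the missing comparison.** The documents give no AE rates, so those below are assumptions. The denominator is the planned 50 per arm (4.2).

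The Wilson limits for 5/50 (10%), with z = 1.960 and z² = 3.841, are

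(0.10 + 3.841/100 ± 1.960 × √(0.10 × 0.90/50 + 3.841/10,000)) / (1 + 3.841/50) = 0.0435 and 0.2136.

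The Newcombe half-width for equal observed rates is

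√((0.10 − 0.0435)² + (0.2136 − 0.10)²) = 0.127, or ±12.7 points.

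The same calculation gives ±15.7 points at 10/50 in each arm and ±17.5 points at 15/50.

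Fisher exact power at 50 per arm, two-sided 0.05, and n per arm for 80% power (normal approximation):

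| Control vs test (assumed) | Power at 50 per arm | n per arm for 80% |
|---|---|---|
| 10% vs 20% | 20% | 199 |
| 10% vs 30% | 64% | 62 |
| 20% vs 40% | 52% | 82 |
| 30% vs 50% | 46% | 93 |

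The comparison can be estimated with an interval, but it would be weak as a hypothesis test.

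**The case against.** The best defence is that 9.1 itself states the comparison, 12.2.2 would tabulate AE frequencies, and all AEs are captured, so a side-by-side table could be produced before database lock. This stands as far as it goes: the events are recoverable. It does not supply the relatedness rule for control-arm events, the dental classification, the denominator or the interval.

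A reader might also infer more than the documents support:

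- **That the risk file replaces the control arm, or that any known harm is accepted.** 12.3.3 never calls the file a comparator and sets no acceptance rule. The wording may mean only that events are classified by hazard. The problem is that 12.3 offers no other basis and leaves this unclear.
- **That dental events are not collected, or are deliberately excluded.** 11.1.2 records all AEs, and 11.1.3 asks for the cause if known and a diagnosis where possible. The word related in 12.3.2 may be shorthand for the wording in 9.1. What is missing is a classification.
- **That the trial will report no comparative safety information.** Default frequencies could be shown by arm. The gap is that the comparison is neither planned nor defined.
- **That the rank sum test is invalid for yes/no events.** 12.2.9 does not prescribe it for AEs. With, say, 15/50 against 5/50 it gives p = 0.0129, against 0.0124 for chi-square (both without continuity correction). Its drawback is that it gives no risk difference or interval.

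**Conclusion.** The concern holds. Section 12.3 does not plan the comparison that 1.1 and 9.1 make the primary safety endpoint, and the relatedness rule in 11.1.4 to 11.1.6 does not allow that comparison to be computed consistently in both arms. This goes beyond missing detail, because the stated basis for evaluation and the stated relatedness rule do not lead to the endpoint.

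No figure in the plan is wrong on this account. The size lies in what the comparison could show: at 50 per arm the 95% CI for the risk difference would be about ±13 to ±18 points if both arms had observed rates of 10% to 30%. Those rates are assumed, and fewer treated subjects would widen the interval. Enrolment is on a convenience basis (sections 4 and 5.3.3) and no allocation method is described, so an unadjusted difference could also reflect differences between the groups.

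**What to change.** 1. **Sections 11.1.4 to 11.1.6 and the eCRF.** Grade relatedness to the assigned aligner, test or control. Add a dental-related classification that matches 9.1, with a definition. It should not widen to every oral or dental event unless the sponsor decides to change the endpoint.
2. **Section 12.3.2.** For all subjects who received an aligner, report per arm the number and percentage with at least one device- or dental-related AE, and with at least one SAE. Give the Nighttime-minus-Daytime risk difference with a 95% CI (Newcombe or Miettinen-Nurminen). State that this is an estimate and not a powered test, and that it is unadjusted, given convenience enrolment and no described allocation method.
3. **Section 12.3.3.** State that the risk file and complaint history are used to classify AEs and put them in context, and that the comparator is the control arm.

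The cost is protocol and SAP wording, one or two eCRF fields and one table. The eCRF change should come early, since consistent classification is hard to restore afterwards.
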